5.4.2 Discontinuation of Study Therapy after CR

Discontinuation of treatment may be considered for subjects who have attained a confirmed CR in the brain, and have been treated for at least 24 months with pembrolizumab.

At the discretion of the investigator, subjects who have discontinued therapy after 24 months and have attained and maintained a CR in the brain, but develop progressive systemic disease may be eligible for up to one year of additional treatment with pembrolizumab via the Second Course Phase, if no additional cancer treatment was administered since the last dose of pembrolizumab, the subject meets the safety parameters listed in the Inclusion/Exclusion criteria, and the trial is open. Subjects will resume therapy at the same dose and schedule at the time of initial discontinuation. Additional details are provided in Section 7.9.

5.4.3 Subject Replacement Strategy

Subjects that are unevaluable will be replaced. Subjects that are unevaluable are those who do not reach the first follow-up imaging time point, 4 weeks after the last day of radiation (see section 6.0)

5.4.4 Clinical Criteria for Early Trial Termination

Early trial termination will be the result of the criteria specified below:

1. Quality or quantity of data recording is inaccurate or incomplete
2. Poor adherence to protocol and regulatory requirements
3. Incidence or severity of adverse drug reaction in this or other studies indicates a potential health hazard to subjects
4. Plans to modify or discontinue the development of the study drug

In the event of Merck decision to no longer supply study drug, ample notification will be provided so that appropriate adjustments to subject treatment can be made.

6.0 SCHEDULE OF EVENTS

	Screening visit: within 28 days of first treatment	Pembro infusion every 3 weeks +15 days	At suspected radiographic progression (+15 days)	At persistent radiographic progression (+15 days)	Safety follow-up: 30 days (+15 days) post discontinuation of pembro	Follow-up: those who complete 2 years of treatment or 35 cycles	Survival: follow-up once off study ⁸
Informed Consent	X						
Inclusion/Exclusion Criteria	X						
Archival Tissue Collection (if available)	X						
Standard of Care Biopsy or Resection of Brain Lesion ¹				X			
Demographics and Medical History	X						
Medication, herbal or dietary supplement review	X		X	X	X	X	
Review Adverse Events, include Events of Clinical Interest ¹⁰			X	X	X	X	
Physical Examination ²	X			X	X	X	
Vital Signs and Weight	X			X	X	X	
ECOG Performance Status	X			X	X	X	
CBC with Differential ³	X	X			X		
Comprehensive Serum Chemistry Panel (with LDH) ³	X	X			X		
Urinalysis	X						
FT4 and TSH ⁴	X	X			X		
PT/INR, aPTT	X				X		
Pregnancy Test (urine or serum/males only – see section 7.6)	X						
Clinical Tumor Imaging	X ⁵					X ⁷	
Ferumoxytol imaging	X ⁶						
24 hr post study drug MRI - Optional	X ⁶						
Biomarker Collection (serum) Optional	X ⁶						
Post-study anticancer therapy status						X	
Survival Status						X	X
Telephone contact							X ⁸

¹Subjects must undergo standard of care biopsy or maximal safe resection as clinically indicated prior to enrollment.

²Physical exam required with every pembrolizumab infusion.

³CBC and CMP (with LDH) to be done every 3 weeks while on pembrolizumab - labs must be done within 28 days before first pembrolizumab infusion, and within 72 hours of subsequent pembrolizumab infusions. Additional labs may be drawn at treating physician's discretion.

⁴FT4 and TSH with every cycle while on pembrolizumab.

⁵Clinical standard of care MRIs are done at baseline, 4 weeks after the last day of radiation and then every 9 weeks (see special instructions below for evaluating persistent radiographic progression). Clinical MRIs may be done more often at physician's discretion.

⁶Ferumoxytol steady state MRIs (within 7 days of clinical standard of care MRIs) are done baseline, 4 weeks after the last day of radiation, anytime there is suspected radiographic progression and 4 weeks after suspected radiographic progression (all timepoints ± 15 days). Serum biomarkers will be obtained ± 15 days of ferumoxytol MRI scan.

⁷ Follow-up after completing 2 years of treatment or 35 cycles (whichever comes later): according to standard of care.

⁸ Survival follow-up once off study: Telephone contact every 12 weeks (± 30 days) to assess for survival status until death, withdrawal of consent, the end of the study, or loss to follow-up, whichever occurs first.

¹⁰Adverse event review will be recorded in Epic continuously while on study. A separate Epic note will be done with each course. All AEs are assessed for attribution to pembrolizumab, ferumoxytol, and standard of care therapy

Trial treatment with pembrolizumab will start on the first day of standard of care radiation (± 15 days) and thereafter every 3 weeks (± 15 days) (dosing delays of up to 7 days are permitted at physician discretion for medical / surgical events or logistical reasons) for up to 2 years or 35 cycles or confirmed radiographic progression, whichever occurs first. Dosing interruptions (missing a dose) are permitted in the case of medical / surgical events or logistical reasons not related to study therapy (e.g., elective surgery, unrelated medical events, subject vacation, and/or holidays), not to exceed two consecutive doses or a maximum of 9 weeks.

Imaging instructions for evaluating persistent radiographic progression: if there is suspected progression, subjects undergo a ferumoxytol steady state MRI and continue on pembrolizumab for one more cycle (total of 4 weeks). At the 4 week point, clinical standard of care and ferumoxytol MRIs will be repeated to confirm persistent radiographic progression. If the 4 week scan confirms progression, then pembrolizumab is discontinued and subject is evaluated for surgery. If histopathology confirms pseudoprogression or is inconclusive, the subject will continue on pembrolizumab every 3 weeks until further radiographic progression is suspected. If histopathology confirms progression, the subject will be removed from the study. If the subject is not a surgical candidate, they will be taken off study and move into the survival follow up stage.

7.0 TREATMENT PLAN AND PROCEDURES

7.1 Participant Screening and Enrollment

In order to participate in this study, signed informed consent must be obtained from the participant. The current Institutional Review Board (IRB) approved informed consent must be signed and dated by each participant prior to undergoing any study procedures or before any prohibited medications are withheld from the participant in order to participate in this study.

7.2 Participant Registration

Participants will be required to give written informed consent to participate in the study before any screening tests or evaluations are conducted that are not part of standard care. Registration from all consented participants must be entered into the OHSU electronic Clinical Research Management System (eCRIS). At a minimum, registration of OHSU participants will include:

- Unique study number
- A completed review of eligibility criteria signed by the Principle Investigator
- Signed copies of the most recently IRB-approved, informed consent form and HIPAA authorization

The Schedule of Events - Section 6.0 summarizes the trial procedures to be performed at each visit. Individual trial procedures are described in detail below. It may be necessary to perform these procedures at unscheduled time points if deemed clinically necessary by the investigator.

Furthermore, additional evaluations/testing may be deemed necessary by the Sponsor and/or Merck for reasons related to subject safety. In some cases, such evaluation/testing may be potentially sensitive in nature (e.g., HIV, Hepatitis C, etc.), and thus local regulations may require that additional informed consent be obtained from the subject. In these cases, such evaluations/testing will be performed in accordance with those regulations.

7.3 Trial Treatments

The treatment to be used in this trial is outlined below in Table 4

Table 4 Trial Treatment

Drug	Dose/Potency	Dose Frequency	Route of Administration	Regimen/Treatment Period	Use
Investigational Agents					
Pembrolizumab	200mg	Every 3 weeks (+15days) (starting on first day of standard of care therapy (+ 15 days)	IV infusion	Day 1 of each 3 week cycle	Experimental
Ferumoxytol	7mg/kg (maximum dose not to exceed 510mg)	Baseline, 4 weeks post radiation, anytime there is	IV infusion	Baseline, 4 weeks post radiation, anytime there is suspected radiographic	Experimental

Drug	Dose/Potency	Dose Frequency	Route of Administration	Regimen/Treatment Period	Use
		suspected radiographic progression and 4 weeks after suspected radiographic progression (all ± 15 days).		progression and 4 weeks after suspected radiographic progression (all ± 15 days).	
Standard of Care Treatments					
Arm 1 only					
Stereotactic radiosurgery	18-35Gy	See section 7.4	See section 7.4	See section 7.4	Standard of care
Arm 2 only					
Radiation	Up to 60Gy	Daily (Monday-Friday) for 6 weeks	See section 7.4	6 weeks	Standard of care
Concurrent temozolomide	75 mg/m ²	Daily (Monday-Sunday) during radiation	Oral	6 weeks	Standard of care
Adjuvant temozolomide	150-200 mg/m ²	First 5 days of a 4 week cycle	Oral	At least 6 months	Standard of care

Timing of Dose Administration

Pembrolizumab: Trial drug treatment should be administered every 3 weeks. All trial treatments will be administered on an outpatient basis. Dosing delays of up to 7 days are permitted at physician discretion for medical / surgical events or logistical reasons. Dosing interruptions (missing a dose) are permitted in the case of medical / surgical events or logistical reasons not related to study therapy (e.g., elective surgery, unrelated medical events, subject vacation, and/or holidays), not to exceed two consecutive doses or a maximum of 9 weeks. The reason for interruption will be documented in the subject's study record. Pembrolizumab will not be administered less than 14 days after any major surgeries including brain biopsy.

Pembrolizumab 200mg will be administered every 3 weeks as per institutional guidelines. The expiration of the reconstituted pembrolizumab is 4 hours at room temperature and 20 hours refrigerated.

The Pharmacy Manual contains specific instructions for the preparation of the Pembrolizumab infusion fluid and administration of infusion solution.

Ferumoxytol (only for study MRIs): The total dose of ferumoxytol will be 7mg/kg (not exceeding 510mg total) per imaging session. The ferumoxytol will be mixed with normal saline 1:1 solution to dilute to 15mg/ml. 1 mg/Kg IV will be injected at the start of the 7th dynamic cycle during the DSC acquisition at a flow rate of 3ml/s followed by 20ml saline flush. The rest of the ferumoxytol will be given as IV injections at a low flow rate (.1ml/s) followed by 20mL saline flush. The flow rates may be adjusted at the physician's discretion.

Vitals monitoring for ferumoxytol MRIs: Blood pressure and pulse will be taken at the start of MRI (\pm 5 minutes), after each ferumoxytol injection (\pm 5 minutes), and again 30 minutes (\pm 5 minutes) after the first injection of ferumoxytol.

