4.3.4.3 Post-Marketing Program- March of 2015 FDA Black Box Warning

In March of 2015 the FDA placed a black box warning on ferumoxytol stating:

WARNING: RISK FOR SERIOUS HYPERSENSITIVITY/ANAPHYLAXIS REACTIONS
Fatal and serious hypersensitivity reactions including anaphylaxis have occurred in patients receiving Feraheme. Initial symptoms may include hypotension, syncope, unresponsiveness, cardiac/cardiorespiratory arrest.

- Only administer Feraheme when personnel and therapies are immediately available for the treatment of anaphylaxis and other hypersensitivity reactions.
- Observe for signs or symptoms of hypersensitivity reactions during and for at least 30 minutes following Feraheme infusion including monitoring of blood pressure and pulse during and after Feraheme administration.
- Hypersensitivity reactions have occurred in patients in whom a previous Feraheme dose was tolerated.

In the black box warning the FDA updated their recommendations of how ferumoxytol should be given. The option to give ferumoxytol (510mg) as a fast undiluted injection in approximately 1 minute has been removed. It was recommended that ferumoxytol (510mg) be given over at least 15 minutes. To accommodate for this, the dose of ferumoxytol in this study will be given in three separate, fractionated doses. The rate of administration of the second and third doses will be slowed down to no faster than 1 mL/s.

Post-Marketing Safety

AMAG's pharmacovigilance system proactively reviews spontaneous reports. Routine surveillance of events is performed daily and monthly signal detection and evaluation processes monitor and update the safety profile. To date the information received from the post-marketing setting is consistent with the known safety profile of ferumoxytol.

As shown in Table 1, cumulative postmarketing reporting rates for serious AESIs (adverse events of special interest) with ferumoxytol since product approval (30 June 2009) have remained low. These event reporting rates are rare and very rare using CIOMS standardized

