Based on communication with AMAG Pharmaceuticals, manufacturer of ferumoxytol, all recommendations apply to iron replacement therapy where infusion rate and dilution do not impact efficacy. However, for an imaging indication certain infusion parameters are required to gain information, such as dynamic imaging. Increased infusion rate will only affect the first injection of 1 mg/kg, which is a small fraction of the full therapeutic dose, and therefore may minimally increase the risk of adverse reactions. The next two injections are given at a slower rate. The recommended 15 minutes has no scientific basis, it has been chosen arbitrarily. For MR imaging stopping the scanner for 15 minutes would be disadvantageous. Applying multiple injections, which is not the case with iron replacement therapy, may increase safety,

compared to continuous injection. This may contribute to the fact that in our patient population only minor adverse reactions have been reported.

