Contrast agents dosing and administration

Clinical Standard of Care MRI: Gadoteridol enhanced MRI will be used per institutional guidelines (see section 8.2.2). In subjects that are already enrolled and have underwent at least one gadolinium enhanced MRI, but do not qualify to get Gadolinium at subsequent imaging time points, non-contrast enhanced MRI can be used as clinical MRI.

Dosing of Gadoteridol: After acquiring precontrast images, gadoteridol (Prohance®, Bracco Pharm) will be injected using a power injector. An IV bolus of 0.1 mmol/kg at a flow rate of up to 3 mL/s will be administered, followed by a saline flush during the first DSC sequence. The appropriate volume of gadoteridol is based on the subject's weight (0.2 ml/kg gadoteridol = 0.1 mmol/Kg) followed by a 20ml saline flush.

Ferumoxytol Imaging

Ferumoxytol imaging consists of two consecutive days of imaging (early and delayed) and will be performed only at time points described in the study schema.

Early intravascular phase scan ferumoxytol imaging

Dosing of ferumoxytol: The total dose of ferumoxytol (AMAG Pharmaceuticals, Inc., Cambridge MA) will be 7mg/kg (not exceeding 510mg total). The ferumoxytol will be mixed with normal saline 1:1 solution to dilute to 15mg/ml. 1 mg/Kg IV will be injected at the start of the 7th dynamic cycle during the DSC acquisition at a flow rate of 3ml/s followed by 20ml saline flush. The rest of the ferumoxytol will be given as IV injections at a low flow rate (1ml/s) followed by 20mg saline flush. The flow rates may be adjusted at the physician's discretion.

Delayed (18-72h) parenchymal phase ferumoxytol scan - Optional

No contrast agent will be given during this MRI. This scan is optional. Every effort will be made to schedule the scan as close to 24 hours after ferumoxytol as possible.

Image processing

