In the Phase II imaging study where ferumoxytol was used as an imaging agent (doses 1.0, 2.5 and 4.0 mg/kg) in subjects with peripheral arterial disease (PAD), there was a possible dose dependent increase in overall TEAEs reported in this study. Only 3.5% of the subject population experienced TEAEs that were related to ferumoxytol. The majority of the treatment-related AEs were mild in severity and were resolved. 6.1% of the subject population experienced SAEs that were eventually resolved; none were treatment related. There were 3 AESIs reported in 3 subjects (2.6%); 1 subject in each dose group experienced 1 AESI. In the 1.0 mg/kg dose group 1 subject experienced acute hypotension. In the 2.5 mg/kg dose group 1 subject experienced a hypersensitivity reaction of rash, and in the 4.0 mg/kg dose group 1 subject experienced a drug hypersensitivity reaction (acute hypersensitivity reaction to ferumoxytol).

Given the potential for hypersensitivity and other adverse reactions observed with other IV anemia therapies, subjects should be monitored for signs and symptoms of hypotension and hypersensitivity following administration of ferumoxytol as outlined in study protocols. Ferumoxytol should only be administered when personnel and therapies are immediately available for the treatment of anaphylaxis and other hypersensitivity reactions.

With certain IV iron preparations, mild to severe low blood phosphorus levels (hypophosphatemia) have also frequently been reported following administration, particularly in women with heavy AUB. Mild to moderate, asymptomatic reductions in blood phosphorus levels have been infrequently observed following ferumoxytol administration.

Elemental iron is essential for normal cell and tissue development, as well as for tumor cell growth. There are no clinical data to suggest that therapeutic IV iron supplementation, given to correct anemia, stimulates tumor development, despite the theoretical risk. While free iron has been implicated in increased oxidative stress, which is potentially associated with cellular damage and carcinogenesis, there are no clinical studies to support that transient increases in oxidative stress resulting from iron supplementation result in increased tumor growth.

Other potential risks to subjects receiving ferumoxytol include the temporary discomfort at the site of injection, as well as the potential for bruising, local infection, and pigmentation following IV administration.

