There are no studies of ferumoxytol in pregnant women, and the risk to a pregnant mother and unborn baby is unknown. In animal studies, ferumoxytol caused fetal malformations and decreased fetal weights at maternally toxic doses of 6 times the human daily dose. Thus ferumoxytol should only be used during pregnancy if the potential benefit justifies the potential risk to the fetus.

It is also unknown whether ferumoxytol is present in human milk. Animal studies showed that when administered daily to pregnant and lactating females, a small amount of ferumoxytol was excreted into breast milk. Because many drugs are excreted in human milk and because of the potential for adverse reactions in nursing infants, a decision should be made whether to discontinue nursing or to avoid ferumoxytol, taking into account the importance of ferumoxytol to the mother and the known benefits of nursing.

No data from clinical trials are available regarding overdose of ferumoxytol in humans. During the post-marketing phase, several subjects received an overdose of ferumoxytol ranging from 1 g in 1 day to 2.5 g over 14 days. Only one case of minor rash was observed.

Although this section provides general guidance regarding the risks and side effects associated with administration of ferumoxytol, investigators should refer to the protocol for study-specific follow-up and the monitoring procedures.

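### The last required vital signs after ferumoxytol are timed from the first of three injections, so the 30 minutes of post-dose monitoring in the boxed warning is not guaranteed

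*Combined protocol and SAP*

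**What the plan says.** Section 4.3.4.3 reproduces the 2015 boxed warning, including this instruction: "Observe for signs or symptoms of hypersensitivity reactions during and for at least 30 minutes following Feraheme infusion including monitoring of blood pressure and pulse". It then says that, to accommodate the updated administration advice, "the dose of ferumoxytol in this study will be given in three separate, fractionated doses", with the second and third no faster than 1 mL/s. The same section argues against following the recommended infusion time: "The recommended 15 minutes has no scientific basis, it has been chosen arbitrarily".

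Section 7.3 gives the dose as 7 mg/kg, at most 510 mg, diluted to 15 mg/mL. The first 1 mg/kg is injected at 3 mL/s during the dynamic acquisition and the rest at 0.1 mL/s. Section 7.6 repeats the scheme with a different rate: "The rest of the ferumoxytol will be given as IV injections at a low flow rate (1ml/s"). Both sections let the physician adjust flow rates.

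Section 7.3 requires blood pressure and pulse at the start of the MRI, "after each ferumoxytol injection (\pm 5 minutes"), "and again 30 minutes (\pm 5 minutes) after the first injection of ferumoxytol". Nothing later is required. The schedule in section 6.0 adds no further ferumoxytol check. Section 9.5.3 gives no duration and points back to the protocol: "subjects should be monitored for signs and symptoms of hypotension and hypersensitivity following administration of ferumoxytol as outlined in study protocols", and "investigators should refer to the protocol for study-specific follow-up and the monitoring procedures".

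**The concern.** The interval matches the warning but the clock starts at the wrong event. The warning counts from the end of the infusion; section 7.3 counts from the first and smallest-exposure step of a three-part dose. A site that follows section 7.3 exactly can therefore take its last required reading less than 30 minutes after the drug has all been given. The window of minus 5 minutes would break the guarantee even for a single injection, since 30 − 5 = 25.

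This is a patient-safety rule that disagrees with a warning the protocol itself quotes. The warning refers to fatal and serious reactions and says that they have occurred in patients who tolerated a previous dose. Subjects here are dosed repeatedly: at baseline, 4 weeks after radiation, at each suspected progression and 4 weeks after that. Sections 7.13 and 9.5.3 remove a subject after an attributable allergic reaction of grade 2 or more, which depends on the reaction being seen.

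**Working it through.** The protocol states no figure for post-dose coverage, so there is none to reproduce. The one derivable input agrees: section 11.0 gives 510 mg in 17 mL, which is 30 mg/mL, and 1:1 dilution gives the stated 15 mg/mL.

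**Inputs.** Total dose = min(7 mg/kg × weight, 510 mg). First injection = 1 mg/kg at 3 mL/s. Remainder at 0.1 mL/s (section 7.3) or 1 mL/s (section 7.6). Last reading at 25, 30 or 35 minutes after the first injection. Assumed: weights of 50 to 140 kg and, to begin with, no gap between injections.

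**Share of dose still to be given after the first injection**
- Up to the cap (510/7 = 72.9 kg): 6/7 = 86%
- 102 kg: (510 − 102)/510 = 80%
- 140 kg: (510 − 140)/510 = 72.5%

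**End of dosing** = first volume/3 + remaining volume/rate. The first injection adds only 1 to 3 seconds. Coverage = reading time − end of dosing.

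| Weight | Remaining | Rate | Dosing ends | Coverage at 25 / 30 / 35 min |
|---|---|---|---|---|
| 50 kg | 300 mg = 20.0 mL | 0.1 mL/s | 3.35 min | 21.6 / 26.6 / 31.6 min |
| 72.9 kg | 437 mg = 29.1 mL | 0.1 mL/s | 4.88 min | 20.1 / 25.1 / 30.1 min |
| 140 kg | 370 mg = 24.7 mL | 0.1 mL/s | 4.16 min | 20.8 / 25.8 / 30.8 min |
| 50 kg | 300 mg = 20.0 mL | 1 mL/s | 0.35 min | 24.6 / 29.6 / 34.6 min |
| 72.9 kg | 437 mg = 29.1 mL | 1 mL/s | 0.51 min | 24.5 / 29.5 / 34.5 min |
| 140 kg | 370 mg = 24.7 mL | 1 mL/s | 0.46 min | 24.5 / 29.5 / 34.5 min |

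Worked line for 72.9 kg at 0.1 mL/s: 510 − 72.9 = 437 mg; 437/15 = 29.1 mL; 29.1/0.1 = 291 s = 4.86 min; plus 1.6 s for the first injection gives 4.88 min; 30 − 4.88 = 25.1 min.

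At the nominal time the shortfall is thus 3.4 to 4.9 minutes at 0.1 mL/s and about 0.5 minutes at 1 mL/s.

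**Effect of a gap.** The documents give no interval between injections for flushing or scanning. Each minute of gap removes one minute of coverage. For illustration at 72.9 kg, an assumed total gap of 5 minutes gives nominal coverage of 20.1 minutes (0.1 mL/s) or 24.5 minutes (1 mL/s); 10 minutes gives 15.1 or 19.5 minutes.

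**The case against.** The strongest reply is that a schedule of readings is not a rule for ending observation. The warning asks staff to watch the patient for 30 minutes; it does not demand a reading at minute 30. Section 7.3 requires vital signs after every injection, including the last, sets no release time and does not forbid longer observation. Local practice may already exceed it. All of that stands, and it is why the finding is that the plan permits a shortfall, not that it imposes one. It does not supply the missing guarantee: no section requires observation or a reading 30 minutes after the last injection, and section 9.5.3 refers back to the protocol.

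A second reply is that section 4.3.4.3 relays the manufacturer's view that the recommendations concern iron replacement, and links any added risk to the fast first injection, so timing from that injection could be deliberate. But the argument there concerns infusion rate, dilution and the 15-minute duration. It never mentions the observation period, which does not interfere with imaging.

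Third, the derivable shortfall is small, the late edge of the window meets 30 minutes if there is almost no gap, part of the worst case comes from the minus 5 minutes and not from the choice of injection, and the larger figures rest on assumed gaps. This is correct. So is the point that section 4.3.4.4 reports 800 infusions at the institution without hypotension, syncope, unresponsiveness or cardiorespiratory arrest. These facts limit how serious the point is; they do not remove the mismatch.

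**Conclusion.** The concern holds. Section 7.3 does not secure the 30 minutes of post-dose monitoring that section 4.3.4.3 quotes, and no reason is given for a different observation time. At 50 to 140 kg with no gap between injections, the last required reading falls 25.1 to 26.6 minutes (0.1 mL/s) or 29.5 to 29.6 minutes (1 mL/s) after dosing ends at the nominal time, and 20.1 to 21.6 or 24.5 to 24.6 minutes at the early edge of the window. At the late edge it falls at 30.1 to 31.6 or 34.5 to 34.6 minutes, so the 30 minutes is then met.

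The weight range and the absence of a gap are assumptions; a gap makes the result worse. No effect on the toxicity estimates is claimed, because sections 5.4.1, 6.0 and 9.4 provide for continuous recording of adverse events, and the primary objective is untouched. It is a safety rule that should be corrected, not a threat to the trial's conclusions.

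**What to change.** Replace the vital-signs sentence in section 7.3 with: *Blood pressure and pulse will be taken at the start of MRI (± 5 minutes), within 5 minutes after each ferumoxytol injection, and again 30 minutes (0 to +10 minutes) after the last ferumoxytol injection; the subject is observed until that reading.* This also removes the minus 5 minutes on the post-injection readings, which as written would allow a reading before the injection it is meant to follow.

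As a secondary tidy-up, state one flow rate for the later injections in sections 7.3 and 7.6, because the end of dosing depends on it.

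The cost is one protocol sentence and the scanner-suite worksheet. Relative to the present nominal time, the extra observation is about 0.5 to 5 minutes per session plus any gap between injections. Assuming 4 sessions for each of 43 subjects (one suspected progression each), 43 × 4 = 172 sessions, and 172 × 5 minutes = 860 minutes, or about 14 hours over the whole trial.

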4.3.4.4 OHSU Toxicity Data for Ferumoxytol

A total of 800 infusions of ferumoxytol have been completed on 410 study subjects as part of OHSU's Blood Brain Barrier sponsored IRB approved protocols. The dose has ranged from 75 to 510 mg of ferumoxytol (0.5 to 11 mg/kg). Toxicities for this group as of May 1, 2017 show no grade 4 or 5 toxicities (CTCAE version 3) that were attributed to ferumoxytol. Three incidents of grade 3 toxicities were possibly attributable to ferumoxytol (one incident of constipation, one of neck pain and one of a rash). The most common adverse events associated with ferumoxytol were 20 (2.5% of total infusions) incidents of mild, transient hypertension and 7 (0.9% of total infusions) incidents of diarrhea. There have been no incidents of hypotension, syncope, unresponsiveness or cardiorespiratory arrest with these 800 administrations of ferumoxytol.

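### The last ferumoxytol vital-sign check is timed from the first injection, so it can come less than 30 minutes after the last one; the post-surgery pembrolizumab restart wording also conflicts with the 14-day rule

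*Combined protocol and SAP*

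**What the plan says.** **Ferumoxytol.** Section 7.3 gives 7 mg/kg per imaging session, capped at 510 mg. A 1 mg/kg bolus comes first, at 3 mL/s, and the remainder follows slowly. Blood pressure and pulse are read at the start of the MRI, after each injection, and finally 30 ± 5 minutes "after the first injection of ferumoxytol".

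Section 4.3.4.3 reproduces the boxed warning, which asks for observation during the infusion and for "at least 30 minutes following Feraheme infusion including monitoring of blood pressure and pulse". The same section states that "the dose of ferumoxytol in this study will be given in three separate, fractionated doses", so the first injection is not the last.

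Section 9.5.3 sets no time of its own. It says that "subjects should be monitored for signs and symptoms of hypotension and hypersensitivity following administration of ferumoxytol as outlined in study protocols" and that "investigators should refer to the protocol for study-specific follow-up and the monitoring procedures". Both sentences lead back to section 7.3, the only place where a post-dose time is given.

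**Pembrolizumab after surgery.** Section 7.3 forbids dosing less than 14 days after major surgery, brain biopsy included. The last paragraph of section 7.4 lets subjects restart within 2 weeks of surgery, calls for discussion with the supplier when a complication prevents that, and sets 30 ± 5 days when pathology suggests pseudoprogression.

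**The concern.** The clock for the last scheduled reading starts when about 80-86% of the drug is still to be given. Staff who follow section 7.3 to the letter can complete every scheduled reading before 30 minutes have passed since the last injection, although the protocol itself reproduces a warning that asks for at least that long. The warning also notes that "Hypersensitivity reactions have occurred in patients in whom a previous Feraheme dose was tolerated", so an uneventful first session is no reason to relax at later ones. Each subject has at least two ferumoxytol sessions, and four with one suspected progression (section 7.6).

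On restart, section 7.4 treats two weeks as a ceiling and section 7.3 treats it as a floor. Read alone, section 7.4 permits dosing that section 7.3 forbids.

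**Working it through.** **Inputs.** Vial 510 mg in 17 mL (section 11.0). Dilution 1:1, dose 7 mg/kg up to 510 mg, first injection 1 mg/kg at 3 mL/s, final check at 25 to 35 minutes (section 7.3). Slow rate 0.1 mL/s in section 7.3 and 1 mL/s in section 7.6; both are within the 1 mL/s ceiling of section 4.3.4.3, so both are carried through.

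**The plan's own figure.** 510/17 = 30 mg/mL; diluted 1:1 this is 15 mg/mL, as stated.

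**Share given first.** 70/490 = 14.3% at 70 kg, and the same at every weight up to 510/7 = 72.9 kg. At 100 kg the cap makes it 100/510 = 19.6%.

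**End of the last injection, 70 kg, no pause, flush time ignored** (both favour the plan).
- First injection: 70/15 = 4.67 mL; 4.67/3 = 1.6 s.
- Remainder: (490 − 70)/15 = 28 mL; 280 s at 0.1 mL/s or 28 s at 1 mL/s.
- End: (1.6 + 280)/60 = 4.69 min, or (1.6 + 28)/60 = 0.49 min.

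**Minutes from the last injection to the final check** = 25, 30 or 35 minus the end time minus any pause. The documents give no pause length, so the non-zero rows are assumptions.

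| Total pause (min) | 0.1 mL/s: earliest / nominal / latest | 1 mL/s: earliest / nominal / latest |
|---|---|---|
| 0 | 20.3 / 25.3 / 30.3 | 24.5 / 29.5 / 34.5 |
| 5 (assumed) | 15.3 / 20.3 / 25.3 | 19.5 / 24.5 / 29.5 |
| 10 (assumed) | 10.3 / 15.3 / 20.3 | 14.5 / 19.5 / 24.5 |

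With no pause, only the last 0.3 min (0.1 mL/s) or 4.5 min (1 mL/s) of the 10-minute window reaches 30 minutes. With five minutes of pause, none of it does at either rate.

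**Other weights, no pause.** From 40 to 120 kg the nominal check falls at 25.1 to 27.3 min (0.1 mL/s) or 29.5 to 29.7 min (1 mL/s), below 30 in every case.

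**Restart rule.** Section 7.3 allows day 14 or later; section 7.4 allows day 14 or earlier. They agree on day 14 only. Confirmed progression leaves the study and pseudoprogression has its own 30 ± 5 days, so after progression surgery the conflict concerns mainly inconclusive pathology. Section 10.0 assumes 32 operated subjects, 26 with true progression, so at most 32 − 26 = 6 would be affected. That ceiling would need all six to be inconclusive, yet section 10.0 expects surgery to supply some pseudoprogression cases. Other major surgery during treatment would add to it.

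**The case against.** **A reading is not an observation period.** The boxed warning sets a period of observation that includes blood pressure and pulse. It does not demand a reading at or after minute 30. Section 7.3 schedules readings after every injection and does not say that the subject is released at the last one. The blood-volume maps also need post-contrast scans, so imaging continues after dosing. This stands. A reader might infer that subjects go unmonitored after most of the dose, or that the warning is necessarily breached; the documents support neither. What they show is that no end of observation is tied to the last injection.

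**The departure was reasoned.** Section 4.3.4.3 cites the manufacturer's view that the recommendations were made for iron replacement, and adds: "The recommended 15 minutes has no scientific basis, it has been chosen arbitrarily". That argument concerns infusion rate and dilution. It offers no reason for shorter observation, so it does not answer the point.

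**The gap is small and the risk is low.** At 1 mL/s without pauses the nominal shortfall is about half a minute, inside the ± 5 minute tolerance. Section 4.3.4.4 reports: "There have been no incidents of hypotension, syncope, unresponsiveness or cardiorespiratory arrest with these 800 administrations of ferumoxytol". Both facts stand, and they make this a minor correction. A reader might multiply the 3/1726 serious hypersensitivity rate in section 9.5.3 by the number of subjects or sessions to count reactions missed. That would count all such reactions, not those falling in the last few minutes, and the documents give no onset by minute.

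**The restart conflict has little reach.** The prohibition in section 7.3 is flat, while section 7.4 is only permissive. This is fair, but a reader of section 7.4 alone would not know it.

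**Conclusion.** The point holds as a minor safety correction. The final scheduled check is tied to the wrong injection. With no pauses, at 70 kg, it nominally comes 4.7 min (0.1 mL/s) or 0.5 min (1 mL/s) short of 30 minutes after the last injection; at the early edge of the window it is 9.7 or 5.5 min short. These figures use the protocol's printed rates, which a physician may adjust. Anything larger depends on pauses that the documents do not state.

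The restart conflict is real and narrow. Neither point touches sample size, precision or the primary endpoint.

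A reader might also go further and infer that the subject-level rule to stop at attributed grade 3 or worse events (sections 5.4.1 and 9.1) should give way to the management tables, because Table 6 continues pembrolizumab in grade 3-4 hypothyroidism. The documents do not support that. The ferumoxytol rules in sections 7.13 and 9.5.3 cover only allergic or anaphylactic reactions, so an event such as the grade 3 constipation or neck pain in section 4.3.4.4 would lose its stop rule. So would pembrolizumab events that are neither immune-related nor infusion reactions. At most, hypothyroidism needs an exception.

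**What to change.** 1. **Section 7.3, vital signs.** Replace the last timing with: observe the subject, with final blood pressure and pulse at least 30 minutes after the end of the last ferumoxytol injection, no minus tolerance. Keep the readings at the start and after each injection. The tolerance matters: moving the anchor but keeping ± 5 minutes would still allow 25. The new wording works at any weight, rate or pause.
2. **Section 7.4, restart.** Replace the two-week limit with no earlier than 14 days after surgery. Keep 30 ± 5 days for pseudoprogression, and keep the supplier discussion when a surgical complication delays restart.
3. **Optional, sections 5.4.1 and 9.1.** Add an exception for hypothyroidism managed under Table 6; otherwise leave the stop rule as it is.

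**Cost.** A wording amendment. Against the nominal time, the final check moves later by 2.7 to 4.9 min (0.1 mL/s) or 0.3 to 0.5 min (1 mL/s) over 40 to 120 kg, plus any pause between injections. No extra scan or visit is needed. The restart change removes only dosing that section 7.3 already forbids.
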